Window		±1h	±1h	±1d	±1h	±1h	±1h	±1d	±1h	±1h	±1d	±1d	±1d	±1d	±1d	±1d	±1d	±1d	±1d	±1d	±1d	+7d	±7d		
Disease Assessments e, h		Refer to Table 1-3																							
Adverse event collection i	X	Recorded from the time of consent through SFU n																					X		
Serious adverse event collection m		Continuously throughout the study																							
Concomitant medications/therapy p		Recorded within 2 weeks from the first dose of study drug through SFU n																							
Survival																							X		

ADA = antidrug antibody; D = day; D/C = discharge; DLT = dose-limiting toxicity; ECG = electrocardiogram; ECHO = echocardiogram; ECOG = Eastern Cooperative Oncology Group; EOT = end-of-treatment; FU = follow-up; LTFU = long-term follow-up; PK = pharmacokinetic(s); SFU = safety follow-up; T1/2 = terminal half-life; UNS = unscheduled; W = week.

Note: Every effort should be made to keep the Schedule of Events on time for each subject.

a An unscheduled visit may occur at any time during the study. Study activities shown will be performed at the investigator's discretion.

b The EOT visit should occur within 30 days after the last dose of AMG 340. If an alternate therapy will be initiated during this period, the EOT visit should be conducted prior to the first dose of alternate therapy.

c Subjects will be admitted for 48 hours **after the infusion on C1D1 and, if implemented, after a second priming dose on C1D5**. If priming doses are **implemented**, subjects will also be admitted for 48 hours on C1D8 (note that a second priming dose may be implemented based on emerging data).

d Vital sign measurements include measurements of diastolic and systolic blood pressure, heart rate, respiratory rate, and temperature. On day 1 dosing, vital signs should be measured prior to study drug administration (up to 10 minutes before), 30 ± 10 minutes after initiation of study drug administration, at completion of study drug administration (±10 minutes), and 1 hour ± 10 minutes after completion of study drug administration; on C1D1 and on **C1D5 and C1D8**, if priming doses have been implemented, vital signs should also be measured 3, 6, and 9 hours ± 10 minutes after completion of study drug administration. Vital signs should be taken after 5 minutes of sitting or lying down.

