#### **6.2.1.2 Dose Priming**

Based on the nonclinical pharmacology of AMG 340, a lower rate of CRS is anticipated than with other T-cell-engaging bispecifics; however, based on the mechanism of action of AMG 340, the most likely DLT to occur is still CRS  $\geq$  grade 3. Cytokine release syndrome will be managed per Principal Investigator discretion and institutional guidelines (a guide for management of CRS is provided in [Table 6-6](#) if institutional guidelines have not been established). Definitions for adverse events, serious adverse events, and DLTs are provided in Section [8.4.6.1.1](#), [8.4.6.1.2](#), and [6.2.1.4.1](#), respectively.

If a grade  $\geq$  3 CRS event occurs in Cohort N (where N represents a Cohort number) during the DLT period, or at the discretion of the DLRT, a dose equal to or less than the dose for Cohort N will be designated as the ‘Priming Dose’ and dose administration in subsequent cohorts (Cohorts N+1 and on) may be modified as follows:

- On Cycle 1 Day 1, subjects will receive the Priming Dose.
- On Cycle 1 Day 8, subjects will receive the full dose corresponding to the cohort in which they have been enrolled.

Note: a second priming dose may be introduced based on emerging data.

If a subject experiences CRS grade  $\geq$  2, or any other grade  $\geq$  2 toxicity after receiving a priming dose that is not unequivocally due to the subject’s underlying malignancy or other extraneous cause, administration of the full dose on cycle 1 day 8 must await approval by the Amgen Medical Monitor(s). At a minimum, CRS must have resolved to

grade  $\leq$  1 before the next is administered. The dose and timing of the full dose for such a subject may be modified at the discretion of the Amgen Medical Monitor and the Investigator; if the subject has their full dose reduced in cycle 1, the subject will be considered DLT-unevaluable and should be replaced. In subsequent cycles, subjects will receive the full dose on day 1.

Following implementation of a priming dose, if administration of the full dose is delayed in cycle 1, the DLT period for that subject should be extended to the same degree (eg, if the full dose is delayed by 4 days, the DLT period will also be extended 4 days). For clarity, treatment-emergent adverse events meeting criteria for a DLT will be treated as a DLT whether they occur after administration of the priming or the full dose.

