##### **6.2.1.4 Toxicity Management**

For the purpose of medical management, all adverse events and laboratory abnormalities that occur during the study must be evaluated by the investigator. The table of clinical toxicity grades from the NCI-CTCAE, Version 5.0 (available on CTEP home page: <http://ctep.info.nih.gov>) is to be used in the grading of adverse events and laboratory abnormalities that are reported as adverse events, each of which will be followed to satisfactory clinical resolution, except for CRS and NT which will be graded according to Lee et al (2019). AMG 340 has not been tested clinically in humans, so the adverse event profile in humans is not known.

Adverse events should be classified as pre-existing or as treatment-emergent adverse events:

- A treatment-emergent adverse event is defined as an adverse event not present prior to initiation of AMG 340 treatment, or an adverse event present prior to AMG 340 initiation that worsens in intensity and/or frequency after initiation of AMG 340 treatment.
- A pre-existing adverse event is an adverse event that does not meet these criteria. Subjects with pre-existing adverse events should be assessed for any underlying illness or other causes and treated as appropriate.

Subjects with treatment-emergent adverse events should also be assessed for intercurrent illness or other causes and treated as appropriate. If a treatment-emergent adverse event is unequivocally due to a subject's underlying malignancy or other extraneous cause, dosing with AMG 340 may be modified at the discretion of the Principal Investigator, following discussion with the Medical Monitors. If a treatment-emergent adverse event is not unequivocally due to the subject's underlying malignancy or other extraneous cause, regardless of whether there is a 'reasonable possibility' that the treatment-emergent adverse event is AMG 340-related, the dose of AMG 340 should be modified as follows:

- For subjects who have completed cycle 1 and have at least clinically or radiographically stable disease (SD, MR, PR or CR) but have experienced a reversible treatment-emergent adverse event, the dose of study drug can be delayed for up to 14 days after the scheduled dosing date. A subject for whom dosing is delayed > 14 days should be discontinued from the study.

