- During any cycle, if a subject develops an ANC < 500/ $\mu$ L, platelets < 10,000/ $\mu$ L, or a hemoglobin < 6.5 g/dL, blood samples must be collected every 3 days and study treatment withheld. Treatment may resume when ANC returns to  $\geq$  1,000/ $\mu$ L, platelet counts return to  $\geq$  50,000/ $\mu$ L or baseline platelet count levels (in subjects with baseline platelets < 50,000/ $\mu$ L), or hemoglobin returns to  $\geq$  8.0 g/dL.
- AMG 340 should be discontinued in any subject who experiences CRS, TLS, or a non-hematologic treatment-emergent adverse event that meets DLT equivalent criteria until resolution of the toxicity to  $\leq$  grade 1 or baseline; thereafter study drug may be resumed with one dose level reduction with Medical Monitor approval.

Up to 2 dose reductions are allowed to manage toxicity; thereafter toxicity will be deemed 'unacceptable' and the subject will be discontinued from therapy. Assessment schedules and cycles are fixed and should continue regardless of whether a dose is held.

While investigator discretion should be used for subject management with regards to toxicities, guidelines for management of CRS and NT are provided in [Table 6-6](#) and [Table 6-5](#).

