##### **6.2.1.4.1.2 Hematologic Dose-limiting Toxicity**

- Grade 3 CRS that does not resolve to  $\leq$  grade 1 within 72 hours or grade 4 CRS.
- Grade 3 TLS that does not resolve to  $\leq$  grade 1 within 72 hours or grade 4 TLS.
- Grade 4 neutropenia for  $> 5$  days or febrile neutropenia.
- Grade 3 thrombocytopenia with bleeding or grade 4 thrombocytopenia.
- Grade 4 anemia.
- Grade 5 adverse events.
- Lymphopenia will not be considered a DLT.

- Adverse events that require a delay in initiation of the next scheduled cycle by > 14 days.

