**Table 6-6. AMG 340 Dose Modification Guidelines for Adverse Events**

Grade	Interruption/Delay	Specific Management	Re-start Guidance	Permanent Discontinuation
Any other AMG 340-related events not meeting DLT criteria				
≥ 3	Interruption/delay required if deemed intolerable and/or clinically significant by the subject or investigator and not responding to appropriate medical management until event has improved to grade ≤ 1	N/A	
 
Re-start possible if successfully managed and improvement to ≤ grade 1 in ≤ 14 days.
 
Delay of next infusion: 
 
≤ 7 days: Administer the delayed infusion (as long as the next scheduled infusion is > 6 days from delayed infusion) and follow the schedule of assessments for the cycle day on which the infusion was originally planned.
 
> 7 days: Skip the delayed infusion and resume schedule of assessments for the next scheduled infusion
 
 
 
Hospitalization: 48 hours
 
Dose modification: Resume at the same dose or reduce to next lower dose if clinically indicated
 
	If subject missed more than 2 consecutive doses of AMG 340 OR In case of reappearance of same event at grade 4 OR In case of repeat grade ≥ 3 event despite dose reduction

Page 13 of 19

Abbreviations and footnotes defined on last page of table.

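### An isolated thrombocytopenia DLT at or above 10,000/µL carries no mandatory hold, sampling interval or recovery level before the optional cycle 1 day 5 dose or the cycle 2 dose

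*Protocol*

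**What the plan says.** Section 6.2.1.4 of the protocol covers treatment-emergent events not clearly explained by the cancer or another outside cause. For these it states that "the dose of AMG 340 should be modified as follows" and gives three bullets.

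- **Delay bullet.** After cycle 1, a subject with at least stable disease and a reversible event can be delayed by up to 14 days. A longer delay means discontinuation.
- **Count bullet.** In any cycle, at ANC below 500/µL, platelets below 10,000/µL or hemoglobin below 6.5 g/dL, "blood samples must be collected every 3 days and study treatment withheld". Restart needs ANC of at least 1,000/µL, platelets of at least 50,000/µL (or a lower baseline), or hemoglobin of at least 8.0 g/dL.
- **Stop bullet.** "AMG 340 should be discontinued in any subject who experiences CRS, TLS, or a non-hematologic treatment-emergent adverse event that meets DLT equivalent criteria" until grade 1 or baseline, then resumption one dose level lower with Medical Monitor approval.

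Section 6.2.1.4.1.2 defines hematologic DLTs by grade or clinical picture. The platelet criterion is "Grade 3 thrombocytopenia with bleeding or grade 4 thrombocytopenia".

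Table 6-6 has no cytopenia row. Its general row for drug-related events of grade 3 or above is headed "Any other AMG 340-related events not meeting DLT criteria". Section 6.2.1.2 adds a Medical Monitor check before the day 8 full dose in priming cohorts.

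**The concern.** The hold rule for blood counts and the definition of a hematologic DLT use different scales, and they do not meet. The count bullet acts on fixed counts. The stop bullet acts on DLT severity but excludes hematologic events. The general row of Table 6-6 excludes events that meet DLT criteria. A platelet DLT at or above 10,000/µL can fall between all three.

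At stake is redosing in a first-in-human study while a platelet DLT is unresolved, with sites free to apply different restart standards to the same event. The ordering is also odd. A subject at 9,000/µL must be held, sampled every 3 days and recover to 50,000/µL. A subject with a grade 4 DLT at 12,000/µL (assuming the grade 4 cut-point lies above that) has none of these requirements.

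**Working it through.** The plan states no figure to reproduce here, so the check is one of rule coverage. Take a subject with a thrombocytopenia DLT, platelets at or above 10,000/µL, and no accompanying CRS, TLS or non-hematologic DLT-equivalent event.

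**1. Rule by rule**

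| Protocol rule | Mandatory hold? | Platelet recovery level? |
|---|---|---|
| 6.2.1.4 delay bullet | No; permits delay after cycle 1 | None |
| 6.2.1.4 count bullet | No; starts below 10,000/µL | 50,000/µL or baseline, only once triggered |
| 6.2.1.4 stop bullet | No; hematologic events not named | Not applicable |
| Table 6-6, other drug-related events | No; events meeting DLT criteria excluded | Not applicable |
| Table 6-6, non-related grade 4 events | Only if judged unrelated, intolerable and not responding | Grade 1 or below within 28 days, in that case only |
| 6.2.1.2, day 8 full dose after a priming dose | Yes, pending Medical Monitor approval | None; the stated minimum concerns CRS |
| 6.2.1.6.1.2 | No; investigator with Medical Monitor, guided by the DLT criteria | None |

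**2. Which doses are affected**

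- No priming: cycle 1 has one dose (Section 6.2.1.4.1), so the next is cycle 2 day 1. No mandatory hold applies.
- Priming: the day 8 full dose is held for approval. The Schedule of Activities also allows a day 5 dose ("if implemented, after a second priming dose on C1D5"), which the approval sentence does not name. The cycle 2 dose is not named either.
- Later cycles and Part B: two readings are possible. If DLT criteria apply only within the 21-day window, the general row of Table 6-6 applies. It gives a conditional interruption and a restart level: "Re-start possible if successfully managed and improvement to" grade 1 or below within 14 days. If DLT criteria are read by severity, as the phrase DLT equivalent in the stop bullet suggests, that row is excluded and the gap continues.

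**3. Monitoring**

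Hematology is done before every dose (Section 4.1), so the count is known. After a finding on cycle 1 day 15, the next scheduled count is cycle 2 day 1, which is day 22: 22 − 15 = 7 days, and the day of the next dose. Under the count bullet it would be every 3 days.

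**4. Size**

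Hold limit divided by restart level:

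- platelets: 10,000 / 50,000 = 0.20
- ANC: 500 / 1,000 = 0.50
- hemoglobin: 6.5 / 8.0 = 0.81

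The CTCAE v5.0 cut-points are not printed. Let X be the assumed grade 4 platelet cut-point. The uncovered grade 4 width is X − 10,000, and its share of the grade 4 range is (X − 10,000) / X.

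| Assumed X (/µL) | Width (/µL) | Share |
|---|---|---|
| 10,000 | 0 | 0% |
| 20,000 | 10,000 | 50% |
| 25,000 | 15,000 | 60% |
| 30,000 | 20,000 | 67% |

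Grade 3 counts lie above grade 4 counts. For any X of 10,000/µL or more, every grade 3 thrombocytopenia with bleeding is therefore outside the platelet hold, even where the grade 4 width is zero.

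**5. Observed events**

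At the 08 March 2022 cut-off, 1 of 23 dosed subjects (1/23 = 4.3%) had DLT events, of neutropenia and thrombocytopenia (Section 2.2.4.3). The counts are not given.

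**The case against.** The strongest reply is that the protocol does not leave these subjects unmanaged. Section 6.2.1.6.1.2 puts continued dosing with the investigator and Medical Monitor and says the DLT criteria are to guide it; those criteria include grade 4 thrombocytopenia. The delay bullet permits postponing the cycle 2 dose. All adverse events must be evaluated and followed to resolution, and unscheduled visits are allowed. Thrombocytopenia and bleeding are listed signs of CRS, and CRS is a stop trigger. Bleeding of grade 3 or above could itself be a non-hematologic DLT-equivalent event. Fixed counts for blood events and grades for other events are also a coherent split.

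Much of this stands. A reader might infer that nothing in the protocol acts on a platelet count above 10,000/µL, or that it requires redosing. The text supports neither. Nor is the Table 6-6 comparison as sharp as it looks, since the general row requires interruption only when the event is judged intolerable or clinically significant and is not responding.

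The hold-to-restart ratios do not prove an error, and the shares in the working are shares of a count range under an assumption, not of subjects. What the reply does not supply is a mandatory hold before the day 5 or cycle 2 dose, or a platelet level at which dosing may resume.

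**Conclusion.** The gap is real and narrow. For an isolated thrombocytopenia DLT at or above 10,000/µL, Section 6.2.1.4 sets no mandatory hold, sampling interval or recovery level before the optional day 5 dose or the cycle 2 dose. Before the day 8 full dose in priming cohorts there is a mandatory hold pending approval, but no platelet level. A literal reading of the count rule permits redosing during a platelet DLT. This is a safety rule worth fixing; it changes no sample size, power or escalation boundary.

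Three wider readings should not be drawn:

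- **All hematologic DLTs.** Febrile neutropenia or grade 4 anemia would be left out in the same way only if the CTCAE definitions allow them at or above the ANC and hemoglobin limits. The documents do not show this.
- **All cycles and Part B.** This holds only if DLT criteria in Table 6-6 are read by severity. SAP Section 6.3.3 confines the DLT-evaluable set to the dose exploration part, which favors the narrower reading without settling it.
- **A case already seen.** The one reported subject's counts are unknown.

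The width of the uncovered grade 4 range depends on the assumed cut-point. The missing rule for counts at or above 10,000/µL does not.

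**What to change.** In the count bullet of Section 6.2.1.4, after the hemoglobin limit of 6.5 g/dL, add: *or any cytopenia meeting the criteria of 6.2.1.4.1.2*. For these events, withhold until the existing restart level for the affected count is met and any associated bleeding or fever has resolved, and resume with Medical Monitor approval. The bullet already applies in every cycle, so the change covers the day 5 dose, the cycle 2 dose and later cycles, and removes the dependence on how Table 6-6 is read. Leave the stop bullet as it is; moving cytopenias there would create a second recovery standard, grade 1 or baseline, beside the count levels.

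The cost is a short insertion at the next amendment, with a resolution condition and an approval step. In practice it means some extra held doses and blood samples every 3 days after a cytopenia DLT. Subjects who do not recover within the existing 14-day delay limit (Sections 6.2.1.4 and 7.1) would be discontinued.

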**Table 6-6. AMG 340 Dose Modification Guidelines for Adverse Events**

Grade	Description of Severity	Interruption/Delay	Specific Management	Re-start Guidance	Permanent Discontinuation
Infusion-related Reaction (continued)					
3	Prolonged (eg, not rapidly responsive to symptomatic medication and/or brief interruption of infusion); recurrence of symptoms following initial improvement; hospitalization indicated for clinical sequelae	Immediate interruption/delay until event has improved to grade $\leq 1$	Consider supportive therapy including steroids as clinically indicated.  Increase monitoring of vital signs as medically indicated until the subject is deemed medically stable.	
 
As for grade 2 infusion-related reaction, with the exception of mandatory dose modification: reduce to next lower dose
 
	If subject missed more than 2 consecutive doses of AMG 340
4	Life-threatening consequences; urgent intervention indicated	N/A	As for grade 3 infusion-related reaction	N/A	Immediately stop the infusion (if applicable) and permanently discontinue AMG 340 (monotherapy or in combination with pembrolizumab) therapy

Abbreviations and footnotes defined on last page of table.

Page 2 of 19

Table 6-6. AMG 340 Dose Modification Guidelines for Adverse Events

Grade	Description of Severity	Interruption/ Delay	Specific Management	Re-start guidance	Permanent Discontinuation
Neurologic Events					
≤ 2	For CRS-related neurological events, use ICANS grading and management system (Section 6.2.1.6.1.1)	Interrupt AMG 340 until the event improves to grade ≤ 1	Follow institutional guidelines for management	Resume AMG 340 no less than 72 hours after the initial observation of the grade 1 or 2 adverse event.	N/A
3			Administer corticosteroids per local practice	Resume AMG 340 no less than 7 days after the initial observation of the grade 3 adverse event. Reduce AMG 340 by 1 dose level.	
 
Initial grade 3 neurologic event does not improve to grade ≤ 1 within 7 days, OR
 
Grade 3 neurologic event reoccurs at the lower dose level within 7 days of re-initiation
 

4		--	--	--	Permanently discontinue AMG 340

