Table 6-6. AMG 340 Dose Modification Guidelines for Adverse Events

Grade	Description of Severity a	Interruption/ Delay	Specific Management	Restart Guidance	Permanent Discontinuation
Cytokine Release Syndrome continued (see Section 6.2.1.6 for additional guidance and grading scale details)					
3	
Symptoms require and respond to aggressive intervention
 
 
Feverb: <math>\geq 38^{\circ}\text{C}</math> WITH
 
Hypotension: requiring a single vasopressor (excluding vasopressin) AND/ORc
 
Hypoxia: requiring high-flow nasal cannulad, facemask, nonrebreather mask, or Venturi mask
 
	Delay AMG 340 until event improves to CRS grade $\leq 1$ .	
Administer:
 
 
Symptomatic treatment (eg, paracetamol/acetaminophen) for fever
 
Supplemental oxygen (high-flow nasal cannula [<math>> 6 \text{ L/min}</math>], facemask, non-rebreather mask, or Venturi mask), as needed
 
A vasopressor <math>\pm</math> vasopressin, as needed
 
Dexamethasone (or equivalent) IV at a dose maximum of (3 doses of 8 mg [24 mg/d]). The dose should then be reduced step-wise.
 
 
AND/OR
 
 
Consider use of tocilizumab (in countries where available) as an additional therapy in this setting at a dose of 4-8 mg/kg as a single dose. Tocilizumab can be repeated for an additional 3 doses with at least an 8 hour interval between doses
 
	
 
The next infusion may be administered if all of the following criteria are met: 
 
The Amgen medical monitor must be consulted prior to re-starting treatment
 
If CRS occurred during AMG 340 infusion, infusion has been interrupted for at least 72 hours
 
The event has resolved to grade <math>\leq 1</math> prior to re-starting treatment
 
 
 
	
If there is no improvement to CRS <math>\leq</math> grade 2 within 5 days and CRS <math>\leq</math> grade 1 within 7 days.
 
In the case of 2 separate grade 3 CRS events.

Page 6 of 19

Abbreviations and footnotes defined on last page of table.

Table 6-6. AMG 340 Dose Modification Guidelines for Adverse Events

Grade	Description of Severity a	Interruption/ Delay	Specific Management	Restart Guidance	Permanent Discontinuation

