4	Life-threatening symptoms • Fever b : $\geq 38^{\circ}\text{C}$ WITH • Hypotension: requiring multiple vasopressors (excluding vasopressin) AND/OR c • Hypoxia: requiring positive pressure (eg, CPAP, BiPAP, intubation, and mechanical ventilation)	N/A	Administer: 
 
Symptomatic treatment (eg, paracetamol/acetaminophen) for fever
 
Supplemental oxygen (positive pressure [eg, CPAP, BiPAP, intubation and mechanical ventilation]), as needed
 
Multiple vasopressors, as needed
 
Dexamethasone (or equivalent) IV at a dose maximum of (3 doses of 8 mg [24 mg/d]). Further corticosteroid use should be discussed with the Amgen medical monitor.
 
Tocilizumab should be administered at a dose of 4-8 mg/kg as a single dose. Tocilizumab can be repeated for an additional 3 doses with at least an 8 hour interval between doses
 
	N/A	Immediately stop the infusion (if applicable) and permanently discontinue AMG 340

Page 8 of 19

Abbreviations and footnotes defined on last page of table.

Table 6-6. AMG 340 Dose Modification Guidelines for Adverse Events

Grade	Description of Severity a	Interruption/ Delay	Specific Management	Restart Guidance	Permanent Discontinuation
Cytokine Release Syndrome continued (see Section 6.2.1.6 for additional guidance and grading scale details)					

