2	• Clinical TLS	Immediate interruption/ delay until event has improved to grade $\leq 1$	TLS should be managed according to the local standard of care and institutional guidelines.	
 
• Restart possible if successfully managed and improvement to <math>\leq</math> grade 1 in <math>\leq 14</math> days
 
• In case of infusion interruption, continue treatment with next scheduled infusion, do not resume prior infusion or administer delayed infusion.
 
• Delay of next infusion: 
 
- <math>\leq 72</math> hours: follow the Schedule of Activities for the cycle day on which the infusion was originally planned. The following infusion should then be administered after 7 (<math>\pm 1</math>) days
 
- <math>> 72</math> hours: skip the infusion and resume Schedule of Activities for the next scheduled infusion
 
 
 
• Hospitalization: 40 to 48 hours
 
	N/A
$\geq 3$	• Clinical TLS	N/A	TLS should be managed according to the local standard of care and institutional guidelines	N/A	Immediately stop the infusion (if applicable) and permanently discontinue AMG 340 therapy

Abbreviations and footnotes defined on last page of table.

Page 10 of 19

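### Protocol 6.2.1.4 allows AMG 340 to restart after events for which Table 6-6 or Section 11.7 requires permanent discontinuation, and no text expressly says which rule governs

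*Protocol*

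**What the plan says.** Section 6.2.1.4 (Toxicity Management) holds AMG 340 for CRS, TLS, or a non-hematologic treatment-emergent event at DLT-equivalent level. Once the event is at grade 1 or lower or back to baseline, "thereafter study drug may be resumed with one dose level reduction with Medical Monitor approval". The section then adds: "Up to 2 dose reductions are allowed to manage toxicity". The restart sentence has no upper grade limit and no exception.

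Table 6-6, under Section 6.2.2, has its own column for permanent discontinuation. For grade 4 CRS it says "Immediately stop the infusion (if applicable) and permanently discontinue AMG 340". For clinical TLS of grade 3 or higher it says "Immediately stop the infusion (if applicable) and permanently discontinue AMG 340 therapy". For a grade 4 infusion-related reaction the instruction is to stop the infusion and "permanently discontinue AMG 340 (monotherapy or in combination with pembrolizumab) therapy" (the combination wording is stray, since both parts of this study are monotherapy). Grade 4 neurologic events also end treatment. The grade 3 CRS row ends treatment if improvement misses its 5-day and 7-day limits, or "In the case of 2 separate grade 3 CRS events".

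For hepatotoxicity, Table 6-6 refers to Section 11.7. That section bars any rechallenge of subjects who clearly meet the permanent-discontinuation criteria of Table 11-3.

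**The concern.** Two sections of one protocol give different answers to the same bedside question: may this subject receive AMG 340 again? Section 6.2.1.4 says yes, at a lower dose with approval. Table 6-6 or Section 11.7 says never.

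This is a first-in-human T-cell engager, and CRS is its identified risk (Table 2-2). As written, a Medical Monitor could rely on Section 6.2.1.4 to approve re-exposure that the dose-modification table forbids, including after life-threatening CRS, TLS, neurotoxicity or infusion reaction.

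**Working it through.** No arithmetic decides this point, so the check sets the rules side by side.

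**Step 1: what the restart sentence reaches.** It applies to treatment-emergent events that cannot be put down wholly to the cancer or another outside cause, whether or not they are thought related to AMG 340. The DLT criteria are in Sections 6.2.1.4.1.1 and 6.2.1.4.1.2. They cover grade 4 CRS, or grade 3 CRS not down to grade 1 within 72 hours; the same for TLS; and non-hematologic events of grade 3 or higher, with listed exceptions. Grade 4 infusion reactions and grade 4 neurologic events are not among those exceptions.

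**Step 2: unconditional overlap.**

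| Event | Section 6.2.1.4 | Table 6-6 |
|---|---|---|
| CRS grade 4 | restart allowed | restart not applicable; stop permanently |
| TLS grade 4, or grade 3 unresolved at 72 hours | restart allowed | restart not applicable; stop permanently |
| Infusion-related reaction grade 4 | restart allowed | restart not applicable; stop permanently |
| Neurologic event grade 4 | restart allowed | stop permanently |

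**Step 3: conditional overlap.** These conflict only when the event follows the stated course and is DLT-equivalent:
- Grade 3 CRS that misses its improvement limits. Any such event is still above grade 1 at 72 hours, because both limits (5 and 7 days, or 120 and 168 hours) fall later, so it is DLT-equivalent.
- A second separate grade 3 CRS event.
- A grade 3 neurologic event that does not improve to grade 1 within 7 days, or recurs at the lower dose within 7 days of restarting.
- A second seizure after restarting. Table 6-3 grades any clinical seizure as at least 3.
- A gastrointestinal event that reappears at grade 4, or repeats at grade 3 or higher despite dose reduction.
- A grade 4 event judged unrelated to AMG 340 that reappears at grade 4. The restart sentence can reach it because relatedness is not required there.
- Hepatotoxicity meeting the permanent-discontinuation criteria of Table 11-3.

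The allowance of two dose reductions matters for the repeat events, because it contemplates a second restart.

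**Step 4: is there a precedence rule?**
- Section 6.2.1.4 points to Tables 6-6 and 6-5 as guidelines, alongside investigator discretion.
- Section 6.2.1.2 offers Table 6-6 as a CRS guide where a site has no institutional guideline.
- Section 6.2.1.6.1.2 leaves continued dosing to the investigator with the Medical Monitor, driven by the DLT criteria, and does not mention the table.
- Section 6.2.2.1 cites Table 6-6 for restart guidance while setting the length of hospital stay.
- Footnote f of Table 6-6 deals with departures from the withholding rules, but is marked only on the Monkeypox and SARS-CoV-2 headers.
- The SAP has no rule on re-treatment.

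None of these expressly ranks the two rules.

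**Step 5: other gates.** Restart needs resolution and approval. A delay of more than 14 days also leads to discontinuation: Section 6.2.1.4 says so for subjects past cycle 1 with at least stable disease, and Section 7.1 lists it as a reason for removal, with a narrow exception. Under every-3-week dosing this leaves 21 + 14 = 35 days from the preceding dose. The limit removes some slow-resolving cases but not an event that resolves within that time.

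**The case against.** The strongest reply is that these are not contradictory commands. Section 6.2.1.4 grants a permission, and Table 6-6 imposes a prohibition. A site that stops permanently breaches neither, and a specific prohibition ordinarily limits a general permission. The layout supports this. The heading of Section 6.2.2 covers restarting and permanent discontinuation, and Section 6.2.2.1 names the table for restart guidance. The table's residual row for other drug-related events is confined to those below DLT level, while the CRS, TLS, infusion-reaction and neurologic rows carry no such limit and so still apply to DLT-level events. Harm would need a sponsor's Medical Monitor to approve what the sponsor's own table forbids.

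Much of this stands: the table is probably meant to govern. It does not settle the matter, because Section 6.2.1.4 is not merely general. It names CRS and TLS and treats the table as guidelines. If the DLT qualifier covers TLS, the TLS-specific criteria reach only grade 4, or grade 3 unresolved at 72 hours. The table bars restart after both, so letting it win would leave the restart permission for non-fatal TLS with nothing to apply to.

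Three stronger readings are not supported:
- A reader might infer that the DLT qualifier attaches only to non-hematologic events, so that CRS and TLS of every grade conflict. That would hold drug for grade 1 CRS until it reached grade 1, and the grade 1 row of Table 6-6 requires no action.
- A reader might count conflicting table rows as a measure of size. Such a count mixes unconditional with conditional conflicts.
- A reader might treat Table 6-5, which has no permanent stop at grade 4, as a further conflict. It is offered as suggested guidance, and its silence contradicts nothing.

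**Conclusion.** The conflict is real and should be fixed. It is an error in a stated rule, not a missing detail. It is unconditional for the four event types in the table above and conditional for the listed repeat, slow-resolving and hepatic events. This rests on reading the restart sentence as written and on the absence of express precedence text, with the placement and cross-references favouring Table 6-6.

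The consequence is for subject safety only. A reader might infer that DLT counts, BOIN decisions, the MTD or the exposure and adverse event tables are affected. The documents do not support that: a DLT is defined by the event, not by what is done afterwards, and the case report form records the action actually taken (Section 11.4).

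No event rate is claimed. Section 2.2.4.3 reports a single grade 3 CRS event and names no grade 4 CRS and no TLS at 08 March 2022. That cut predates the current amendment, the list is not stated to be exhaustive, and a rate would not bear on a wording conflict.

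**What to change.** Add to the restart sentence in Section 6.2.1.4: *except for events for which Table 6-6 or Section 11.7 requires permanent discontinuation; these requirements take precedence and such subjects must not be rechallenged*. This follows the approach that Section 11.7 already takes for liver injury. State also that footnote f of Table 6-6 stays in force for the infection rows.

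Keep the one-level dose reduction and Medical Monitor approval for all other events. Do not write instead that Table 6-6 governs restart in general. For grade 3 CRS, its restart guidance requires no dose reduction and says only "The Amgen medical monitor must be consulted prior to re-starting treatment", so a general statement would remove two safeguards that Section 6.2.1.4 provides.

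The cost is a short addition in a protocol amendment, with no change to data collection, sample size or analysis. The downside is that the Medical Monitor loses discretion to re-treat in these rare cases, including a subject who has recovered and is responding.
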